10.3.2.1. Adverse Event Overview

An overview of adverse events will be presented for each treatment group consisting of the number and percentage of patients experiencing at least one event for the following adverse event categories:

- Any treatment-emergent adverse event;

- Treatment-emergent adverse events with a "possibly related", "probably related", "definitely related" of being related to AVXS-101
 - Any AE reported as Possibly, Probably, or Definitely Related will be consolidated into a single category and summarized as "Related" in the tables
 - Any AE reported as Unlikely Related or Unrelated will be consolidated into a single category and summarized as "Not Related" in the tables
- Grade 3 and 4 treatment-emergent adverse events;
- Serious treatment-emergent adverse events;
- Treatment-emergent adverse events leading to discontinuation of patient from study;
- Treatment-emergent adverse events leading to death;
- Deaths.

For each adverse event presented in the overview by overall.

For the final analysis tables (i.e., after database lock of the study), just the two relatedness categories ("Related", "Not Related") will be presented.

For an interim run of this table (i.e., using an interim data cut), it is possible that there will be AEs with unknown relationship present. If this situation occurs, the table will present a third row ("Unknown") in addition to "Related" and "Not Related" and the AEs with unknown relationship will be summarized in the "Unknown" row. If there are no AEs with unknown relationship in the interim cut of data, the "Unknown" row in the table will not be included.

Data listings, patient narratives, etc. will present the relationship to study treatment as collected on the CRF.

10.3.2.2. Adverse Event by SOC and PT

The following summaries of adverse events will be generated:

- Treatment-emergent adverse events;
- Treatment-emergent adverse events occurring in two (2) or more patients;
- Treatment-emergent adverse events categorized as "related" to AVXS-101;
- Serious treatment-emergent adverse events;
- Grade 4 treatment-emergent adverse events;
- Grade 3 or 4 (see definition below) treatment-emergent adverse events;
- Treatment-emergent adverse events leading to discontinuation of patient from study;
- Treatment-emergent adverse events leading to death;
- Treatment-emergent adverse events leading to concomitant medication use (events with other action taken of "concomitant medication prescribed").

For all adverse event summaries, the number of treatment-emergent adverse events, the number and percentage of patients experiencing treatment-emergent adverse events will be tabulated according to SOC and PT. Patients reporting more than one adverse event for a given PT will be counted only once for that term (most severe incident for the severity tables and most related incident for the relationship tables). Patients reporting more than one

adverse event within a SOC will be counted only once for that SOC. Patients reporting more than one adverse event will be counted only once in the overall total.

A listing by treatment group of treatment-emergent adverse events grouped by body system and preferred term with patient numbers will be created.

10.3.2.3. Adverse Event by PT

The number of treatment-emergent adverse events and the number and percentage of patients experiencing treatment-emergent adverse events will be tabulated according to preferred term and sorted by overall frequency. Similar summaries will be provided for Grade 3 and 4 treatment-emergent adverse events and treatment-emergent adverse events with a "possibly related" to AVXS-101 categorization.

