3.4. Safety Objectives

The safety objectives are to:

- Evaluate the safety of AVXS-101 in patients with SMA Type 1
- Determine the safety of AVXS-101 based on the development of unacceptable toxicity defined as the occurrence of any Common Terminology Criteria for Adverse Events (CTCAE) [CTCAE 04] Grade 3 or higher, unanticipated, treatment-related toxicity.

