10.3.2.7. Adverse Events by Maximum Relationship

Treatment-emergent adverse events also will be summarized by maximum relationship of each preferred term to study drug (AVXS-101), as assessed by the investigator. If a patient has an adverse event with unknown relationship, then the patient will be counted in the relationship category of "unknown," even if the patient has another occurrence of the same event with a relationship present. The only exception is if the patient has another occurrence of the same adverse event with a relationship assessment of "possibly related" or higher. In this case, the patient will be counted under the "related" category.

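### Section 10.3.2.3 limits the by-preferred-term table of drug-related events to those rated possibly related, against the SAP's own pooled definition of related

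*SAP*

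**What the plan says.** Section 10.3.2.3 of the SAP plans three tables by preferred term. The first has no restriction on grade or relatedness: all treatment-emergent adverse events (TEAEs) "will be tabulated according to preferred term and sorted by overall frequency". Two subsets follow. One is by grade: "Similar summaries will be provided for Grade 3 and 4 treatment-emergent adverse events". The other is by relatedness: "treatment-emergent adverse events with a 'possibly related' to AVXS-101 categorization".

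Four other sections deal with relatedness:
- Section 10.3.2.1: "Any AE reported as Possibly, Probably, or Definitely Related will be consolidated into a single category". That category is labelled Related, and the final tables are to carry only Related and Not Related.
- Section 10.3.2.2 plans a SOC and preferred-term table of events in the related category.
- Section 10.3.2.5 names all three ratings when it defines the related events to be summarized by maximum grade.
- Section 10.3.2.7 treats a rating of possibly related or higher as related.

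On grade, the overview in Section 10.3.2.1 has a line for "Grade 3 and 4 treatment-emergent adverse events", and Section 10.3.2.2 lists "Grade 3 or 4 (see definition below) treatment-emergent adverse events". The safety objective in Section 3.4 uses a different threshold: "Grade 3 or higher, unanticipated, treatment-related toxicity".

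**The concern.** The table restricted to related events and sorted by frequency is where a reader looks to see which events are attributed to the product and how often. As worded, it takes one of the three ratings that the SAP counts as related, and the two it leaves out are the stronger attributions.

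This is a single-arm trial of up to 20 patients, so a few patients move a percentage visibly and there is no concurrent control group in which a wrong filter would show up. A programmer who follows Section 10.3.2.3 to the letter would produce a related-event table that can contradict those built under Sections 10.3.2.1 and 10.3.2.2, and the SAP does not say which one governs.

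A smaller uncertainty concerns grade. Section 10.3.2.2 points to a definition of its Grade 3 or 4 category that does not follow, and none of the adverse-event sections says where a Grade 5 event is counted.

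**Working it through.** The SAP gives no figure to reproduce here. The check sets the table definitions side by side and then bounds the possible discrepancy.

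**Relatedness filter by section**

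| SAP section | Table | Ratings counted as related |
|---|---|---|
| 10.3.2.1 | Overview | possibly, probably, definitely |
| 10.3.2.2 | SOC and preferred term | the pooled related category |
| 10.3.2.3 | Preferred term, sorted by frequency | possibly only |
| 10.3.2.5 | Maximum grade | possibly, probably, definitely |
| 10.3.2.7 | Maximum relationship | possibly or higher |

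Four of the five agree. Section 10.3.2.3 stands alone, and a possibly-only table also does not fit the rule that final tables show just two relatedness categories.

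**Direction.** For a given preferred term, let *r* be the number of patients with at least one event in any of the three ratings, and *a* the number with at least one event rated possibly related. Every patient in *a* is also in *r*, so *a* ≤ *r*. The literal table shows *a*/N where the pooled rule shows *r*/N. The shortfall (*r* − *a*)/N is never negative.

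**A possible aggravation.** Section 10.3.2.2 counts a patient once per preferred term, at the most related incident, in the relationship tables. If that rule carries over to Section 10.3.2.3, a patient with one possibly and one definitely related event of the same term is classed as definitely related and leaves the table altogether. The count then falls to *a′*, the patients whose highest rating is possibly related, with *a′* ≤ *a* ≤ *r*. The SAP does not say whether the rule carries over.

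**Size.** Section 3.5 gives up to 20 patients. With N = 20, one omitted patient is 1/20 = 5 percentage points; with fewer patients it is more. The split of ratings is not known. Assume *r* = 6 patients with one preferred term, each with a single rating:

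| Assumed split (possibly / probably / definitely) | Pooled rule | Literal Section 10.3.2.3 | Shortfall |
|---|---|---|---|
| 6 / 0 / 0 | 6/20 = 30% | 6/20 = 30% | 0 points |
| 2 / 2 / 2 | 6/20 = 30% | 2/20 = 10% | 20 points |
| 0 / 3 / 3 | 6/20 = 30% | 0/20 = 0% | 30 points |

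The range runs from no difference to complete omission. These rows illustrate the mechanism and do not predict a result.

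**What remains visible elsewhere.** Probably and definitely related events stay in the unrestricted preferred-term table of Section 10.3.2.3, in the related table of Section 10.3.2.2 and in the maximum-grade summary of Section 10.3.2.5. The defect is confined to one table.

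**Grade.** Sections 10.3.2.1, 10.3.2.2 and 10.3.2.3 all use Grades 3 and 4 as the category. No definition follows in Section 10.3.2.2; Section 10.3.2.6, further down, describes how grades are assigned but does not define that category. Read literally, the category excludes Grade 5. Fatal TEAEs have their own overview line in Section 10.3.2.1, which also has a line for deaths, and their own table in Section 10.3.2.2. The maximum-grade tables in Sections 10.3.2.5 and 10.3.2.6 state no upper limit at Grade 4.

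**The case against.** The strongest reply is that Section 10.3.2.1 already governs. It sets the pooling for the tables in general and allows only two relatedness categories at the final analysis, so the wording in Section 10.3.2.3 is most naturally read as a leftover for the pooled category. Section 21.5 fits that reading: it records the collapsing of ratings in Section 10.3.2.1 and lists no matching change to Section 10.3.2.3. No hypothesis test, efficacy endpoint or collection of events is affected, and every related event is reported in at least one other table. All of this stands. It makes the point a correction of wording, but it does not remove the contradiction, because a table specification should not depend on the programmer guessing which section prevails.

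Three stronger readings are tempting, and the SAP does not support them.
- A reader might infer that the by-preferred-term tables show only possibly related and Grade 3 and 4 events. They do not: Section 10.3.2.3 first tabulates all TEAEs, and the two subsets are additional.
- A reader might infer that fatal events drop out of the report, or that the Grade 3 and 4 rows breach a definition of severe events as Grade 3 or higher. Fatal events are tabulated separately. The threshold in Sections 3.4, 4.3 and 6.2.4.4 belongs to unacceptable toxicity, which must also be unanticipated and treatment-related. It is a different construct from the table category, which is used consistently. It is fair to say that no listed table gives a single patient count at Grade 3 or higher, but separate reporting of Grades 3 and 4 and of fatal events is a legitimate choice if it is stated.
- A reader might infer that events with missing causality should be counted as Related, because Section 10.3.2.1 provides an unknown row only for interim runs. That would be a new imputation rule, and it would conflict with Section 10.3.2.7, which puts such patients in an unknown category unless another occurrence of the same event is rated possibly related or higher. It is not needed here.

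**Conclusion.** The contradiction is real and narrow. In one planned table, Section 10.3.2.3 uses a filter for related events that is stricter than the SAP's own definition and omits the two stronger attributions. Taken literally, it can understate related incidence by preferred term and cannot overstate it. The understatement lies anywhere from zero to the full related count, depending on ratings that the SAP cannot foresee; the only fixed unit is one patient in at most 20, or at least 5 points. The conclusion assumes that the table is programmed as written; if the programmer applies Section 10.3.2.1 instead, no error arises. On grade, what remains is minor: a promised definition is missing and the place of Grade 5 events is not stated.

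**What to change.** In Section 10.3.2.3, replace the possibly related restriction with Related, spelled out as possibly, probably or definitely related, so that it matches Sections 10.3.2.1, 10.3.2.2, 10.3.2.5 and 10.3.2.7.

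As minor additions, put the promised definition of the Grade 3 or 4 category into Section 10.3.2.2 and state once, for Sections 10.3.2.1 to 10.3.2.3, where Grade 5 events are counted. Either make the category Grade 3 or higher, or keep Grades 3 and 4 and say that fatal TEAEs are tabulated separately. Either choice works if the same one is used in all three sections.

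The cost is a few words and the matching table filters and titles. No data collection, test or sample size changes. The relatedness correction can only leave the counts in that table unchanged or raise them.

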10.3.2.4. Adverse Events of Special Interest

The following specific treatment-emergent adverse events of special interest, which may be searched using Standardized MedDRA queries, will be summarized:

- Hepatotoxicity, identified via the following SMQs:
 - Hepatic failure, fibrosis and cirrhosis and other liver damage-related conditions (SMQ)
 - Hepatic disorders (SMQ)
- Thrombocytopenia, identified via the following SMQs/HLT:
 - Hematopoietic thrombocytopenia (SMQ)
 - Haemorrhages (SMQ)
 - All TEAEs which code into the "Platelet disorders NEC" HLT
- Cardiac events, identified via the following SMQs:
 - Ischemic heart disease (SMQ)
 - Cardiomyopathy (SMQ)
 - Cardiac arrhythmias (SMQ)
 - Embolic and thrombotic events (SMQ)
 - Myocardial infarction (SMQ)
- Ganglionitis, with potential cases identified by reviewing all TEAEs which code to the "Nervous System Disorders" SOC

For each AE of interest category, the number and percentage of patients experiencing at least one TEAE in the search for the event of interest will be presented overall. AEs of interest will be summarized by SOC and PT overall.

10.3.2.5. Related Adverse Events by Maximum Grade

Treatment-emergent adverse events and treatment-emergent adverse events with a "possibly related", "probably related", or "definitely related" of being related to AVXS-101 will be summarized by maximum grade of each preferred term. If a patient has an adverse event with unknown grade, then the patient will be counted in the grade category of "unknown," even if the patient has another occurrence of the same event with a grade present.

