10.3.2.6. Adverse Events by Maximum Severity Grade Level

Treatment-emergent adverse events will be summarized by maximum CTCAE grade level of each preferred term. Each preferred term will be assigned to a grade level based on severity and seriousness, adapted from CTCAE Version 4.03 for grading severity of adverse events.

All serious adverse events will be categorized according to Grade definition.

If a patient has a non-serious adverse event with unknown grade, then the patient will be counted in the severity grade level category of "unknown," even if the patient has another occurrence of the same event with a grade present.

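### In the maximum-grade tables an ungraded occurrence displaces a known Grade 3 or higher occurrence of the same event, without the exception that the SAP gives the relationship table

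*SAP*

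**What the plan says.** Four subsections of SAP Section 10.3.2 bear on this.

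- **10.3.2.2 (by SOC and PT)** sets the counting rule for all adverse event summaries. A patient counts once per preferred term, taking the "most severe incident for the severity tables and most related incident for the relationship tables".
- **10.3.2.5 (maximum grade)** covers all treatment-emergent events and those related to AVXS-101. They "will be summarized by maximum grade of each preferred term". One ungraded occurrence sends the patient to the unknown row, and this applies "even if the patient has another occurrence of the same event with a grade present". No known grade is exempt, and it does not matter whether the ungraded occurrence is serious.
- **10.3.2.6 (maximum severity grade level)** has a narrower trigger: only an ungraded occurrence that is non-serious sends the patient to the unknown row. The section also says: "All serious adverse events will be categorized according to Grade definition".
- **10.3.2.7 (maximum relationship)** starts from the same unknown rule but protects a known occurrence judged at least possibly related: "The only exception is if the patient has another occurrence of the same adverse event with a relationship assessment of" that level or above. Such a patient is counted as related.

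**The concern.** A table headed by maximum grade should not drop a grade that has been recorded. Under Section 10.3.2.5, a patient with a documented Grade 3 event and one ungraded recurrence of the same term leaves the Grade 3 row. Within the rows for Grade 3 and above, the override can only lower a count.

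The relationship table shows that the authors met the same masking problem and guarded against it: a known adverse finding beats a missing one. The grade tables have no equivalent guard, and no reason is given.

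The related-event half of Section 10.3.2.5 matters most. The safety objective (Section 3.4) and the primary safety endpoint (Section 4.3) concern treatment-related toxicity of Grade 3 or higher. This is the adverse event table closest to them.

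**Working it through.** The SAP states no figure to reproduce, so the check applies each rule to test cases and then sizes one misplaced patient.

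**Test cases.** One patient, one preferred term, two occurrences. The last column is the rule proposed under the fix.

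| Case | 10.3.2.2 | 10.3.2.5 | 10.3.2.6 | Proposed |
|---|---|---|---|---|
| A. Grade 3 non-serious, plus ungraded non-serious | Grade 3 | Unknown | Unknown | Grade 3 |
| B. Grade 3 or higher serious, plus ungraded non-serious | Known grade | Unknown | Not settled: the override is triggered, but serious events are to be categorized by grade | Known grade |
| C. Grade 3, plus ungraded serious | Grade 3 | Unknown | Override not triggered | Grade 3 |
| D. Grade 1, plus ungraded non-serious | Not settled: the ungraded occurrence might be the more severe | Unknown | Unknown | Unknown |

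In cases A to C the general rule and Section 10.3.2.5 give different answers for the same patient. In cases B and C, Sections 10.3.2.5 and 10.3.2.6 can also differ from each other, although both tabulate all treatment-emergent events by maximum grade.

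**Is the severe event counted elsewhere?**

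- All-cause Grade 3 and 4 events: yes. There is an overview row in 10.3.2.1, SOC and PT tables in 10.3.2.2 and a PT table in 10.3.2.3.
- Serious and fatal events: yes, in 10.3.2.1 and 10.3.2.2.
- Related events by grade: no other tabulation is shown in Section 10.3. Sections 10.3.2.1 to 10.3.2.3 tabulate related events and Grade 3 or 4 events separately and do not cross them.

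**Size.** Section 3.5 allows up to 20 patients, and all who are infused enter the Safety Population (Section 5.1).

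- Shift per affected patient = 1/N.
- N = 20: 1/20 = 5.0 percentage points.
- N = 15 (assumed, to show the range): 1/15 = 6.7 percentage points.
- Example at N = 20: two patients have a Grade 3 event under one term, and one of them also has an ungraded recurrence. The Grade 3 row shows 1/20 = 5% instead of 2/20 = 10%.

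The number of such patients cannot be derived, because the SAP gives no rate of missing grades.

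**The case against.** The strongest reply has four parts.

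1. **Severe events remain visible elsewhere.** A reader might infer that they vanish from the safety report. The documents do not support that. All-cause Grade 3 and 4, serious and fatal events have their own tables, none of which states an unknown-grade override. The patient also stays in the unknown row, and the listings keep the individual events. This part stands for all-cause events but not for related events by grade. One loose end remains: Section 10.3.2.2 plans a table of "Grade 3 or 4 (see definition below) treatment-emergent adverse events" without a clear definition following. Nothing shows that the override is meant to apply there.
2. **Section 10.3.2.6 is narrower.** A reader might infer that Grade 3 to 5 events are lost equally from both sections. Only a non-serious ungraded occurrence triggers the rule in 10.3.2.6. A fatal event is serious, and the sentence on serious events can be read as keeping it in its grade row. This stands, although the SAP does not say which rule takes precedence.
3. **A specific rule may refine a general one.** Section 10.3.2.2 is silent on missing grades, and with one grade missing the true maximum of a non-fatal event is not known. That is a fair defence of unknown when the known grade is low. It is weak when the known grade is already 3 or higher, because the patient then certainly belongs at that level or above.
4. **Missing grades may be rare.** Section 4.6.1 has all adverse events assessed for severity, and in a trial this small gaps can be queried before lock. This limits the likely frequency; it does not make the rule right.

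**Conclusion.** The point holds in limited form. Section 10.3.2.5 states a rule that gives a wrong count whenever a known Grade 3 or higher occurrence is paired with an ungraded one. It conflicts with the general counting rule and lacks the exception written for the relationship table. Section 10.3.2.6 shares the defect for non-serious ungraded occurrences and leaves precedence open for graded serious ones.

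The consequence is confined to descriptive tables. A reader might infer that the primary safety endpoint or an efficacy conclusion is affected. Neither is: Section 6.2.4.4 takes the safety endpoint from the case report form, and no hypothesis test uses these tables. What is at risk is the one tabulation shown in Section 10.3 that crosses relatedness with grade, at 5 percentage points per affected patient if 20 are treated. Whether any patient will be affected depends on grades still missing at database lock, which the SAP does not give.

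**What to change.** Add the same exception to the unknown-grade sentence in Sections 10.3.2.5 and 10.3.2.6: *except that if another occurrence of the same preferred term has a known Grade 3 or higher, the patient is counted at the highest known grade.* Keep unknown where the highest known grade is 1 or 2. List or footnote every ungraded occurrence, so that the missing information stays visible.

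A simpler rule, under which any known grade wins, is not advised. It would report a Grade 1 plus ungraded pair as maximum Grade 1, although the ungraded occurrence could be severe. The restricted exception follows the logic of Section 10.3.2.7, where only the adverse category overrides unknown.

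The cost is one clause in each of two sections, one more programming rule and a footnote or listing. No further data collection is needed.
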